6.4. Exploratory/Other Endpoints Analysis

6.4.1. Definition

The exploratory endpoints are:

7. MULTIPLE COMPARISONS AND MULTIPLICITY

No multiplicity adjustment is needed since there is no hypothesis testing in this study, Bayesian methods for primary endpoint and secondary endpoint #1 and descriptive nature of all other endpoints.

8. SAFETY ANALYSIS

8.1. General

In this study, safety will be assessed by qualified study personnel by evaluating reported adverse events, adverse device effects, vital signs measurements, and use of concomitant medications.

No clinical laboratory tests, physical examinations, and ECGs are scheduled to be performed during this study.

The safety analysis set will be used for all safety analyses. Summaries will be presented by treatment group and for all patients.

8.2. Duration of Exposure to IMP

Since the dosing of the test IMP is on an as-needed basis, there is no set maximum exposure.

Duration of exposure to IMP is the number of days from date of the 2nd dose (since the 1st dose is used for testing at the study site on date of randomization) to date of last dose of IMP (last dose of IMP date – 2nd dose of IMP date + 1). If the 1st dose is not used on date of randomization, the duration of exposure to IMP will be calculated as last dose of IMP date – 1st dose of IMP date + 1 assuming no testing is done at study site for the patient. Number and percent of patients will be summarized by duration of exposure to IMP categories \leq 1 week, >1 to ≤ 2 weeks, ..., >11 to ≤ 12 weeks, and $>$ week 12. Duration of exposure to IMP (days) and number of inhalations will also be summarized as continuous data using descriptive statistics.

The number of days a patient takes IMP will be summarized as continuous data using descriptive statistics. If a patient takes more than 1 IMP treatment on the same day, the patient will be counted only once in the summary; if a patient does not take any IMP treatment on a given day the patient will be counted as zero on that day.

8.3. Inhalation Flow Parameters

Inhalation flow parameters (peak inhalation flow [PIF], inhalation volume, inhalation duration, and time to PIF) values will be calculated for each week in the treatment period.

The inhalation parameters for each week are defined as the values from the inhalation with the median value of PIF during each week. If the number of inhalations is an even number, the later of the two inhalations in the middle will be deemed as the inhalation for the week. If no inhalations are done in a week, no inhalation parameters are defined for the week. Similarly the inhalation parameters for the entire 12-week treatment period are the values from the inhalation with the median PIF during the entire 12-week treatment period. Any inhalation with PIF $>$ 120 L/min will be excluded from derivations.

Summary statistics for inhalation flow parameters will be presented by week in the treatment period, and the entire 12-week treatment period. Actual values and changes from week 1 to each week and overall will be summarized using descriptive statistics.

Statistical analyses of inhalation flow parameters will be performed outside of the scope of this SAP. The big data team will analyze this data and a separate SAP will be developed for this.

8.4. Adverse Events

All adverse events will be coded using the MedDRA. Adverse events occurring on or after the treatment start date will be included in the summary tables while all of the adverse events will be listed in data listings.

A summary will be presented for adverse events in the following categories: all adverse events, adverse events determined by the investigator to be related to study drug, severe adverse events, serious adverse events, adverse events leading to withdrawal from the study, non-serious adverse events, device-related adverse events (DS group only), asthma related adverse events, and CAE related adverse events. The incidence of patients with an adverse event in each category will be summarized using descriptive statistics.

Summaries will be presented for all adverse events (overall and by severity), adverse events determined by the investigator to be related to study drug (overall and by severity), serious adverse events, adverse events leading to withdrawal from the study, non-serious adverse events, and device-related adverse events (DS group only).

The incidence of adverse events will be summarized using descriptive statistics by SOC and preferred term (all AEs overall will also be presented by just preferred term category). Patients are counted only once in each SOC category, and only once in each preferred term category. For the summaries by severity, patients are counted at the greatest severity. Adverse events with the missing flag indicating serious will be excluded from the summary of serious adverse events but included in the summary of non-serious adverse events.

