7.1.5.3. Reporting a Serious Adverse Event

7.1.5.3.1. Investigator Responsibility

To satisfy regulatory requirements, all serious adverse events that occur during the study, regardless of judged relationship to administration of the IMP, must be reported to the sponsor by the investigator. The event must be reported within 24 hours of when the investigator learns about it. Completing the serious adverse event form and reporting the event must not be delayed, even if not all the information is available. The investigator does not need to actively monitor patients for adverse events once this study has ended.

Serious adverse events occurring to a patient after the last administration of IMP of that patient has ended should be reported to the sponsor if the investigator becomes aware of them.

The serious adverse event form should be sent to the local safety officer (LSO) or designee (a CRO in a country without a sponsor LSO) (contact information is in the Clinical Study Personnel Contact Information section); the LSO will forward the report to the sponsor's GPSP.

The following information should be provided to record the event accurately and completely:

- study number
- investigator and investigational center identification
- patient number
- onset date and detailed description of adverse event
- investigator's assessment of the relationship of the adverse event to the IMP (no reasonable possibility, reasonable possibility)

Additional information includes:

- age and sex of patient
- date of first dose of IMP
- date and amount of last administered dose of IMP
- action taken
- outcome, if known
- severity
- explanation of assessment of relatedness
- concomitant medication (including doses, routes of administration, and regimens) and treatment of the event
- pertinent laboratory or other diagnostic test data

- medical history
- results of dechallenge/rechallenge, if known
- for an adverse event resulting in death
 - cause of death (whether or not the death was related to IMP)
 - autopsy findings (if available)

Each report of a serious adverse event will be reviewed and evaluated by the investigator and the sponsor to assess the nature of the event and the relationship of the event to the IMP, study procedures, and to underlying disease.

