9.7. Safety Analysis

Safety analyses will be performed using the safety analysis set. For categorical variables, patient counts and percentages will be provided.

Safety assessments and time points are provided in [Table 3](#).

All adverse events will be coded using the Medical Dictionary for Regulatory Activities (MedDRA). Each patient will be counted only once in each preferred term or System Organ Class (SOC) category for the analyses of safety. Summaries will be presented for all adverse events (overall and by severity), adverse events determined by the investigator to be related to test IMP (ie, reasonable possibility; defined as related or with missing relationship [Section [7.1.4](#)]; overall; and by severity), serious adverse events, adverse events causing withdrawal from the study, and adverse device effects. Summaries will be presented by treatment group and for all patients. Patient listings of serious adverse events and adverse events leading to withdrawal will be presented.

Changes in vital signs measurements data will be summarized descriptively. All values will be compared with predefined criteria to identify potentially clinically significant values or changes, and such values will be listed.

The use of concomitant medications will be summarized by therapeutic class using descriptive statistics.

For continuous variables, descriptive statistics (n, mean, standard deviation, median, minimum, and maximum) will be provided for observed values and changes from baseline to each time point. For categorical variables, patient counts and percentages will be provided. Descriptive

summaries of serious adverse events, patient withdrawals due to adverse events, adverse device effects, and potentially clinically significant abnormal values (vital signs) based on predefined criteria will be provided as well.

If any patient dies during the study, a listing of deaths will be provided, and all relevant information will be discussed in the patient narrative included in the CSR.

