If data are processed from other sources (eg, central laboratory, bioanalytical laboratory, central image center, electronic diary data, electronic patient-reported outcome [ePRO] tablet), these data will be sent to the investigational center, where they will be retained but not transcribed to the CRF, unless otherwise noted in the protocol. These data may also be sent electronically to the sponsor (or organization performing data management). All patient data must have supportive original source documentation in the medical records, or equivalent, before they are transcribed to the CRF. Data may not be recorded directly on the CRF and considered as source data, unless the sponsor provides written instructions specifying which data are permitted to be recorded directly to the CRF.

For patients who enter a study but do not meet entry criteria, at a minimum, data for screening failure reason, demography, and adverse events from the time of informed consent will be entered in the CRF.

Data Quality Control

Data Management is responsible for the accuracy, quality, completeness, and internal consistency of the data from this study. Oversight will be carried out as described in the sponsor's SOPs for clinical studies. Day to day data management tasks for this study are delegated to a contract organization, and these functions may be carried out as described in the SOPs for clinical studies at that organization. These SOPs will be reviewed by the sponsor before the start of data management activities.

Data will be verified by the study monitor using the data source, and reviewed by Data Management using both automated logical checks and manual review. Data identified as erroneous, or data that are missing, will be referred to the investigational center for resolution through data queries. Any necessary changes will be made in the clinical database, and data review and validation procedures will be repeated as needed. Data from external sources will be compared with the information available in the CDMS and any discrepancies will be queried.

Applicable terms will be coded according to the coding conventions for this study.

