11. CHANGES TO ANALYSES SPECIFIED IN THE STUDY PROTOCOL

There are no changes to analyses specified in the study protocol.

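### SAP 8.4 counts adverse events with a missing seriousness flag as non-serious, so each arm's serious event count can be too low but never too high; the practical effect is probably close to nil

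*SAP*

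**What the plan says.** SAP section 8.4 (Adverse Events) gives an explicit rule for a missing seriousness flag: "Adverse events with the missing flag indicating serious will be excluded from the summary of serious adverse events". The second half of that sentence then says where such events go instead: "but included in the summary of non-serious adverse events". The protocol has no rule of its own for this case.

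For a missing relationship to the study product the protocol does have a rule. Section 9.7 (Safety Analysis) gives the related category as "defined as related or with missing relationship", and the synopsis says the same. SAP 8.4 names the table only as "adverse events determined by the investigator to be related to study drug (overall and by severity", without repeating the rule. SAP section 11 states: "There are no changes to analyses specified in the study protocol". The protocol's relationship rule is therefore best read as still in force.

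Three provisions limit how often the seriousness rule can operate and what it can do:
- SAP 8.4 also says that "all of the adverse events will be listed in data listings".
- Protocol Appendix G says: "Data identified as erroneous, or data that are missing, will be referred to the investigational center for resolution through data queries".
- Protocol section 7.1.5.3.1 says of serious adverse events: "The event must be reported within 24 hours of when the investigator learns about it".

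**The concern.** A blank flag means that seriousness was not recorded. It does not mean that someone judged the event non-serious. Protocol section 7.1.5.1 makes an event nonserious when it meets none of the listed criteria, and a blank does not record that assessment. The SAP rule treats it as if it did.

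The same safety analysis therefore sends an unknown relationship to the worse category and an unknown seriousness to the better one. Neither document gives a reason for the difference. Safety of the inhaler is secondary objective #5 and serious events are likely to be few, so the serious event table is one where a single patient would show. What is at stake is the accuracy of that table in the final report.

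**Working it through.** The plan states no figure on this point, so there is none to reproduce. The check is a comparison of the two rules, a bound, and an illustration of scale.

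**1. The two missing-data rules**

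| Missing field | Source | Counted as | Possible error in the worse category |
|---|---|---|---|
| Relationship | Protocol synopsis and 9.7 | Related | Too high or correct |
| Seriousness | SAP 8.4 | Non-serious | Too low or correct |

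**2. Bound on the serious event count in one arm**

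Let s be the number of patients with at least one event flagged serious. Let m be the number of further patients who have no event flagged serious but at least one event with a blank flag. Assume that the recorded flags are correct.

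- The SAP rule reports s.
- Counting blanks as serious reports s + m.
- The true number lies between s and s + m.

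The SAP figure is always the lower end of the range, and the two rules agree only when m = 0. The non-serious summary can be too high because of the same events.

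**3. Difference between arms**

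With subscripts D for the digital system arm and C for control, the true difference lies between s_D − (s_C + m_C) and (s_D + m_D) − s_C. The reported difference, s_D − s_C, sits inside that interval. The one-way error therefore holds within each arm; the comparison between arms could move in either direction.

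**4. Scale (illustration only)**

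Planned enrolment is 330 at 1:1 (SAP 2.4 and 2.2), so 330 / 2 = 165 per arm. The values of s and m are assumed, because the documents give neither.

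| s | SAP rule, s/165 | Blanks as serious, m = 1 | Blanks as serious, m = 3 |
|---|---|---|---|
| 0 | 0.00% | 1/165 = 0.61% | 3/165 = 1.82% |
| 2 | 2/165 = 1.21% | 3/165 = 1.82% | 5/165 = 3.03% |
| 4 | 4/165 = 2.42% | 5/165 = 3.03% | 7/165 = 4.24% |

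At m = 0 the columns coincide. The digital system safety set requires at least one dose (SAP 3.3), so its denominator may be a little below 165 and the percentages a little higher.

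**The case against.** The strongest case for leaving the rule alone has three parts.

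**The rule will rarely have anything to act on.** Missing data are queried, and under Appendix G database lock acknowledges that the data are complete and accurate, with investigator approval. Serious events also reach the sponsor on their own form within 24 hours, and asthma exacerbations have a separate CRF page with source documentation (Protocol 7.1.1). This stands, and it is why the expected effect is near zero. It does not justify the direction of the rule, which applies only to flags that survive those steps. The SAP does not require those flags to be reconciled with the serious event reports before lock.

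**The two fields need not share a default.** Relationship is an investigator's judgement with no second source. Seriousness follows listed criteria and has its own reporting stream, and serious status requires a criterion to be met. This is a fair distinction, and it weakens the argument from consistency alone. It does not turn an unassessed event into one that was found to meet no criterion.

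**Reversing the rule creates the opposite error.** Counting every blank as serious could put a trivial event in the serious table with no serious event report behind it. This stands too, and it is why reconciliation has to come first.

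A reader might also infer that the rule hides serious events, or that the absence of a Data Monitoring Committee makes it more dangerous. The documents support neither. An affected event stays in the all-event tables, including those by severity, and in the listings. The rule governs final tables produced after the end of the study (SAP 2.5.2), while ongoing review uses serious event reports as they arrive (Protocol 3.4). A committee would not change what this sentence does.

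**Conclusion.** The point holds as a minor one. Under SAP 8.4 the serious event count in each arm is correct or too low and never too high, provided that the recorded flags are correct. That is opposite in direction to the protocol's rule for a missing relationship.

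The size is 0.6 percentage points per affected patient at 165 per arm, and the expected number of such patients is near zero. That expectation rests on the query and reporting procedures working as described; the documents give no count of missing flags. The safety summaries are descriptive, and the primary analysis is untouched.

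Two further inferences should not be drawn. The rule does not bias the comparison between arms in a known direction. Nor does the SAP's silence on missing relationship show that the protocol's rule was dropped, since SAP section 11 declares no changes.

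**What to change.** Replace the sentence in SAP 8.4 with a rule in two steps:

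1. Before database lock, query every missing seriousness flag and reconcile it with the serious adverse event reports.
2. Stop counting any flag still missing as non-serious. Either include the event in the serious adverse event summary and mark it in the listing, or show it in a separate row labelled as seriousness missing.

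While the section is open, restating the protocol's missing-relationship rule there would remove any doubt that it applies.

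The cost is a sentence or two, plus one for the relationship rule, with no new data collection. The downside is that an unresolved event that was in truth not serious could slightly raise the serious count, by the same 0.6% of an arm per patient, and so differ from the sponsor's serious event reports. The mark or the separate row makes any such difference visible. If no flag is missing at lock, the tables do not change.

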8.5. Deaths

If any patient dies during the study, all relevant information will be discussed in the patient's narrative included in the CSR.

8.6. Vital Signs

Summary statistics for vital signs (pulse, systolic and diastolic blood pressure, and respiratory rate) will be presented at baseline, and the end of treatment and ET visits. Vital signs values and changes from baseline to each visit will be summarized using descriptive statistics.

Summaries of potentially clinically significant abnormal values will include all postbaseline values (including scheduled, unscheduled, and early termination visits). The incidence of potentially clinically significant abnormal values will be summarized using descriptive statistics with the criteria specified in [Table 1](#).

[Table 1](#) specifies the criteria for identifying vital signs as potentially clinically significant abnormal values. Note that in order to qualify as potentially clinically significant abnormal, a value needs to meet both criteria below: ie, have a value beyond the criterion value and a change of at least the magnitude specified in the change relative to baseline column.

Table 1: Criteria for Potentially Clinically Significant Vital Signs

Vital Sign	Criterion value	Change relative to baseline
Pulse	≥ 120 bpm	Increase of ≥ 15 bpm
	≤ 50 bpm	Decrease of ≥ 15 bpm
Systolic blood pressure	≥ 180 mm Hg	Increase of ≥ 20 mm Hg
	≤ 90 mm Hg	Decrease of ≥ 20 mm Hg
Diastolic blood pressure	≥ 105 mm Hg	Increase of ≥ 15 mm Hg
	≤ 50 mm Hg	Decrease of ≥ 15 mm Hg
Respiratory rate	<10 breaths/min	

8.7. Concomitant Medications or Therapies

Concomitant medications and therapies, including medications that are taken on an as needed basis and occasional therapies, will be monitored during the study. Details of prohibited medications may be found in Section 5.6 of the study protocol. All concomitant medications will be coded using the WHO drug.

The incidence of concomitant medications and therapies will be summarized using descriptive statistics by therapeutic class category and preferred term. The incidence of concomitant medications for asthma at baseline will also be summarized using descriptive statistics by therapeutic class category and preferred term. Patients are counted only once in each therapeutic class, and only once in each preferred term category. Concomitant medications will include all medications taken from the day of treatment start through the end of treatment.

9. TOLERABILITY VARIABLES AND ANALYSIS

Tolerability is not applicable to this study.

10. STATISTICAL SOFTWARE

All data listings, summaries, and statistical analyses will be generated using SAS® version 9.4 or later.

11. CHANGES TO ANALYSES SPECIFIED IN THE STUDY PROTOCOL

There are no changes to analyses specified in the study protocol.

